7.3.3. Replacement of Patients

Subjects will not be replaced.

8. TREATMENT OF SUBJECTS

8.1. Description of Subject Device

KeraStat Cream is a non-sterile, non-implantable, emollient-based wound dressing intended to act as a protective covering in the management of a variety of skin conditions.

Version: 00

Effective Date:

03-01-2018

8.2. Concomitant Medications and Therapies

8.2.1. Pharmacological Therapy

Concomitant medications are permitted during this study unless otherwise specified in the Exclusion Criteria.

8.3. Randomization

Patients will be randomized to receive standard of care or KeraStat Cream.

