At the Screening/Baseline Visit (Visit 1, Week 0), following informed consent, initial eligibility will be verified per the inclusion/exclusion criteria and demographics and brief medical history will be collected. Subjects will be randomized to receive standard of care or KeraStat Cream. A physical exam and photograph of the area to be irradiated will be obtained, and subjects will complete the Dermatology Life Quality Index.

During the course of radiation therapy (4-6 weeks) and for the duration of the post RT treatment period (4-week follow up), subjects will complete a daily diary detailing symptoms and treatment details. Weekly from week 2 of RT until the end of treatment, study staff will assess the subject for radiation dermatitis by recording the RTOG for Radiation-Induced Acute Skin Toxicity scores and taking photographs. The same evaluation will be performed at the follow up visit after treatment. Subjects will complete the Dermatology Life Quality Index at each visit.

Inclusion Criteria:

Subjects must meet all of the following criteria:

- 1. Age ≥ 18
- 2. Female
- 3. Diagnosis of early stage (stage 0-2) breast cancer and scheduled to receive 4-6 weeks of fractionated radiation therapy as part of breast conserving therapy following lumpectomy

Exclusion Criteria:

Version: 00 03-01-2018

Effective Date:

Name of Company:Name of Product:Type of Study:KeraNetics, LLCKeraStat® CreamClinical Proof of Concept

To participate in the study, subjects must not meet any of the following criteria:

- 1. Previous radiation therapy to the area to be treated with radiation therapy
- 2. Receiving palliative radiation therapy
- 3. Low dose radiation protocol
- 4. Unhealed or infected surgical sites in the irradiation area
- 5. Patients undergoing cytotoxic chemotherapy or concurrent Herceptin as part of overall treatment plan (tamoxifen/aromatase inhibitor allowed)
- 6. Use of oral corticosteroids or topical corticosteroids in the irradiation area
- 7. Subjects with an autoimmune disease affecting the skin (e.g., scleroderma, systemic lupus erythematosus, psoriasis) are excluded. A history of other autoimmune disease that does not have direct skin involvement (e.g. rheumatoid arthritis, inflammatory bowel disease, multiple sclerosis) does not exclude participation on the study unless the subject requires active treatment with systemic steroids, immune suppression or biologic agents, or systemic chemotherapeutic agents (methotrexate or cyclophosphamide).

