4.2. Rationale

Although well tolerated by most patients, about 30% of patients undergoing RT develop a Grade 2 or worse early adverse skin reaction (EASR). One study in Taiwan showed 23% of patients

Version: 00

techniques, a significant number of patients experience skin toxicity⁴.

Effective Date: 03-01-2018

undergoing chest wall or whole breast irradiation developed moist desquamation based on the RTOG scale⁵. This scale described grade 2 skin toxicity as tender or bright erythema, patchy moist desquamation / moderate erythema; Grade 3 skin toxicity was described as confluent moist desquamation other than skin fold, pitting edema. Both grade 2 and 3 skin toxicities were recorded in the assessment of patients in the Taiwanese study. Another study comparing breast IMRT to conventional tangent fields showed a decrease in moist desquamation, as defined by the NCI CTC version 2, from 48% to 31% of patients, suggesting that even with advanced treatment

For this study, we will classify grade 2 or 3 skin toxicity (per the RTOG scale) as an EASR. Beyond the discomfort patients may experience, EASRs may result in poor patient outcomes. Severe EASRs can require a "treatment break" which, in some cancers, may result in incomplete tumor control and greater chance of local recurrence and lower survival rates. In addition to the potential impact on cancer outcomes, EASRs may affect patients' self-esteem due to the appearance of their skin and recovery time after treatment. Standard skin regimens often include routine application of creams or lotions in an effort to combat the dryness, prevent interruption of the skin's natural barrier (e.g., cracking or flaking), and reduce the appearance of inflammation. Patients often begin using these creams/lotions at the start of RT. Providing patients with a product that moisturizes and reduces the appearance of inflammation may improve patients' satisfaction with their appearance as they progress through RT treatment.

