6. INVESTIGATIONAL PLAN

6.1. Overall Study Design

This is a single site, between subject, open-label comparison pilot study to assess the feasibility and effectiveness of KeraStat Cream in managing RT skin toxicity. The length of study participation for a subject is 8-12 weeks depending on when a subject returns for her final follow-up evaluation. The Study Design Schematic is shown below in Figure 1 with the Acceptable Study Windows in Table 2.

Sufficient subjects will be screened such that 24 total subjects will complete the study. Patient compliance is expected to be good, so a target recruitment of 26 subjects is desired.

Once a RT patient is determined to be a candidate for inclusion in this study, they may be approached for consent to participate. A total of 26 breast cancer patients scheduled to receive RT will be recruited and consented.

RT will begin 4 to 10 weeks after surgery; the targeted volume will be the ipsilateral breast with or without regional lymph nodes. Once the patient has consented to participate in the study, their baseline pre-RT assessments can be completed during the radiation treatment-planning process.

Patients are generally treated with RT Monday through Friday, with weekends and holidays off, for approximately 4 to 6 weeks. Patients will be provided with KeraStat Skin Cream for application as often as needed but at least twice daily, morning and evening.

During the course of treatment, the patient sees the radiation oncologist weekly in clinic to review the patient's treatment course, monitor the skin's appearance after application of KeraStat Skin Cream or standard of care, and answer questions. Breaks in the treatment schedule should be avoided whenever possible, but breaks necessitated by RT skin toxicity or for other reasons will be recorded. The radiation oncologist will see each patient in follow-up 4-8 weeks after completing RT to assess the patient for RT-induced skin and other toxicities that may have occurred.

Version: 00

Effective Date: 03-01-2018

Figure 1: Study Design Schematic

Table 2: Acceptable Study Windows

Visit	Day Visit	Acceptable Visit Window
Screening (Visit 1)	Day 1	None
Baseline (Visit 1)	Day 1	None
First evaluation (Visit 2)	RT Day 8	±2 days
Second evaluation (Visit 3)	RT Day 15	±2 days
Third evaluation (Visit 4)	RT Day 22	±2 days
Fourth evaluation (Visit 5)	RT Day 29	±2 days
Fifth evaluation (Visit 6)	RT Day 36	±2 days
Final evaluation (Visit 7)	Post RT Day 30	±14 days

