6.5. Study Procedures

6.5.1. Visit 1

After obtaining consent, ensuring the subject meets study inclusion/exclusion criteria, and randomizing the subject, study personnel will photograph the site to be irradiated. Study personnel will collect vital signs. Subjects will complete the Dermatology Life Quality Index. Study personnel will provide KeraStat Cream to subjects randomized to receive KeraStat Cream. Subjects randomized to standard of care will follow the instructions of their radiation oncologist. Study personnel will provide subjects with a daily diary form where subjects will note symptoms or treatment details of concern.

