7. SELECTION AND WITHDRAWAL OF SUBJECTS

7.1. Subject Inclusion Criteria

At the Screening Visit (Visit 1), subjects must meet all of the following criteria:

- 1. Age ≥ 18
- 2. Female
- 3. Diagnosis of breast cancer and scheduled to receive 4 to 6 weeks of radiation therapy (radiation dose of 42 Gy or more)
- 4. Able and willing to sign protocol consent form
- 5. Able and willing to document symptoms and treatment details as often as needed, not to exceed daily notes
- 6. Able and willing to have photographs of the affected area taken regularly

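### RT dose, fractions, technique and nodal field are not listed as data and the RTOG and DLQI tests are unadjusted, so a chance imbalance in RT exposure would bias the observed effect estimate

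*Combined protocol and SAP*

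**What the plan says.** **Allocation.** Section 8.3 reads "Patients will be randomized to receive standard of care or KeraStat Cream". Section 12.2 adds equal allocation, 12 per group. No section names a stratification factor, blocking or an allocation method.

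**RT exposure.** Section 7.1 admits a woman "scheduled to receive 4 to 6 weeks of radiation therapy (radiation dose of 42 Gy or more"), with no upper limit on dose. Under Section 6.1, "the targeted volume will be the ipsilateral breast with or without regional lymph nodes". The synopsis is narrower. It asks for "Diagnosis of early stage (stage 0-2) breast cancer and scheduled to receive 4-6 weeks of fractionated radiation therapy" after lumpectomy, and it excludes a "Low dose radiation protocol". Section 7 repeats neither limit, and the synopsis gives no dose figure.

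**Data.** Sections 6.5, 10 and 11 cover photographs, vital signs, RTOG and other skin assessments, DLQI, diaries, demographics, brief medical history, cream use and adverse events. Total dose, fractions, technique and nodal field are not among them. The only RT item to be recorded is treatment breaks (Section 6.1). The diary's treatment details are not defined as RT data.

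**Analysis.** Section 12.1 compares DLQI and RTOG between arms by t-test, with no covariate. The synopsis lists the maximum RTOG grade among its secondary evaluations. Table 2 places the on-RT evaluations at RT Days 8, 15, 22, 29 and 36.

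**The concern.** Radiation is the exposure that produces the skin reaction. If one arm happens to receive more of it, the observed difference in RTOG or DLQI mixes that imbalance with any effect of the cream. The planned test does not separate the two, and the listed data would not show an imbalance in dose, technique or field.

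Course length adds a second route. A maximum taken over more gradings can only stay the same or rise, so subjects on longer courses have more chances to record a high grade whatever they apply to the skin.

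The results at stake are the effectiveness comparisons and the SDs and event rates. Collecting data to design a larger trial is a primary objective, and Section 12.1 feeds these summaries into the next power calculation. The compliance estimate does not depend on RT balance between arms.

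**Working it through.** **1. The plan's own figures (Section 12.2).**
- Two-sample t-test, 12 per group, difference 1.2 SD, two-sided 0.05 (the level is assumed, since the plan states none). Noncentrality 1.2 × √(12/2) = 2.94 on 22 df gives power 80.2%, against the stated 80%.
- Margin of error for compliance: 1.96 × √(0.25/12) = 0.283, as stated.

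Both reproduce.

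**2. Number of on-RT gradings.** Take a Monday start on Day 1 and treatment Monday to Friday (Section 6.1).
- A 4-week course ends on Day 26 and reaches Days 8, 15 and 22: three gradings.
- A 6-week course ends on Day 40 and reaches Days 8 to 36: five gradings.

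This fits the synopsis total of 5 to 7 visits: baseline, three to five on RT, and follow-up.

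**3. Chance of imbalance.** Let K of 24 subjects have a binary RT factor (for example the longer course), with 12 per arm and no stratification. The number x in one arm is hypergeometric:

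P(x) = C(K, x) × C(24−K, 12−x) / C(24, 12), with C(24, 12) = 2,704,156.

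For K = 12, a gap of 4 or more means x ≤ 4 or x ≥ 8: 2 × (1 + 144 + 4,356 + 48,400 + 245,025) / 2,704,156 = 0.220.

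For K = 6, it means x ≤ 1 or x ≥ 5: 2 × (18,564 + 190,944) / 2,704,156 = 0.155.

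| K of 24 with the factor | P(gap of 4 or more) | P(gap of 6 or more) |
|---|---|---|
| 6 | 15.5% | 1.4% |
| 8 | 19.3% | 2.7% |
| 10 | 21.4% | 3.6% |
| 12 | 22.0% | 3.9% |

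These count both directions. Half of each favours a given arm.

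**4. What an imbalance does.** The documents give no effect of course length, dose or field on the scores, so a shift of 0.5 to 1.5 within-stratum SD is assumed. Bias = (gap/12) × shift. The false-positive rates come from simulation (100,000 runs per cell, no cream effect, K = 12).

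| Split | Shift (SD) | Bias (SD) | False positives, unadjusted | False positives, adjusted |
|---|---|---|---|---|
| 6 v 6 | 0.5 / 1.0 / 1.5 | 0 | 4.3% / 2.9% / 1.4% | about 5% |
| 8 v 4 | 0.5 / 1.0 / 1.5 | 0.17 / 0.33 / 0.50 | 6.0% / 8.3% / 10.5% | about 5% |
| 9 v 3 | 0.5 / 1.0 / 1.5 | 0.25 / 0.50 / 0.75 | 8.3% / 16.4% / 27.3% | about 5% |

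Averaged over all allocations, the unadjusted test holds 5.0% (checked at shifts of 1.0 and 1.5 SD). Balanced draws run below 5% and unbalanced draws above it. Adjusting for the factor brings the bias to zero at every split.

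**5. Effect of adjustment on power.** With a 6 v 6 split and a true difference of 1.2 total SD, power is 81%, 82% and 84% unadjusted against 82%, 88% and 94% adjusted, for shifts of 0.5, 1.0 and 1.5 SD. No increase in N is needed.

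**The case against.** **Randomization already allows for this.** Chance imbalance is part of the sampling error that the t-test accounts for, and the overall type I error is 5%. That stands. A reader might infer that the plan inflates the false-positive rate, or that a positive result would probably be an RT artefact. The documents support neither. The harm is conditional on the imbalance actually drawn, is moderate at 8 v 4, and is larger only at splits such as 9 v 3, which are uncommon.

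**The RT course is not wholly hidden.** Breaks are recorded, the count of on-RT visits roughly shows course length, scheduled dose must be checked at entry, and Section 16.1 ties the CRF to medical records. So it would go too far to say that imbalance could never be shown or adjusted for. Dose, fractions, technique and nodal field are unlisted, not unobtainable.

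**The cited technique comparison.** A reader might use the fall in moist desquamation from 48% to 31% in Section 4.2 to size the problem. It compares IMRT with conventional fields on NCI CTC version 2, whereas this trial grades by RTOG. No section says that both techniques are used at this single site. It says nothing about course length, and stratifying on course length would not balance technique.

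**It is a small pilot.** Feasibility comes first and the effectiveness results are described as descriptive. This weighs against requiring stratification, which in an open-label single-site study can also make assignments easier to predict. It does not weigh against recording the exposure, because designing the next trial is also a primary objective.

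**Conclusion.** The point holds as a gap in data capture and adjustment, not as a flaw in the validity of the randomized comparison. With 12 per arm, a gap of 4 or more subjects on a binary RT factor has a 15.5% to 22.0% chance if 6 to 12 of 24 subjects have it. At 8 v 4 the observed difference is then biased by 0.17 to 0.50 SD under assumed shifts of 0.5 to 1.5 SD, with 6.0% to 10.5% false positives given that split. The RT mix and the size of the shift are assumptions, since the documents give neither. The unequal number of gradings, about three against five, follows from Table 2. Even if the arms balance, SDs and event rates pooled over an unrecorded RT mix are harder to carry to a trial with a different mix.

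**What to change.** - **Section 6.5:** transcribe from the existing RT record the planned and delivered total dose, number of fractions, technique, nodal field and interruptions.
- **Section 12.1:** tabulate these by arm. Compare RTOG and DLQI in a linear model with treatment and planned course length (shorter v longer, cut-point fixed in advance) as the one prespecified covariate. Tabulate RTOG and moist desquamation by course length.
- **Optional, Section 8.3:** blocked randomization stratified by planned course length, with concealed and varying block sizes because the study is open-label at a single site.
- **Eligibility wording:** reconcile the RT criteria in the synopsis with those in Section 7, so that the intended RT mix is clear.

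The cost is a few fields copied from a record that already exists and one residual degree of freedom (22 to 21). The covariate deals with course length only. Imbalance in technique, dose or nodal field would be visible in the tables but not adjusted for, which is a reasonable limit with 24 subjects.

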9. STUDY DEVICE MATERIALS AND MANAGEMENT

9.1. Study Device

KeraStat Cream is a non-sterile, non-implantable, emollient-based wound dressing intended to act as a protective covering in the management of a variety of skin conditions. KeraStat Cream is designed to be topically applied to the skin surface. When applied, KeraStat Cream covers the skin or wound, isolating it from the external environment, absorbing excess exudate and facilitating a moist wound environment.

9.2. Study Device Packaging and Labeling

KeraStat Cream will be provided in multiuse tubes. The study device supplies will be maintained at the site under controlled conditions and dispensed by qualified personnel at the study site. The study device labels will contain information to meet the applicable regulatory requirements.

9.3. Study Device Storage

The study device must be stored at room temperature (15 to 30°C [59-86°F]). The study device must be dispensed or administered according to procedures described herein. Only subjects enrolled in the study may receive the study device, in accordance with all applicable regulatory requirements. Only authorized site staff may supply the study device.

9.4. Study Device Preparation

KeraStat Cream final product will be manufactured within applicable current Good Manufacturing Practice (cGMP) regulations in accordance with KeraNetics quality system. The product will be supplied in the form of a cream and packaged in a multi-use tube as detailed in Section 9.2.

9.5. Administration

KeraStat Skin Cream has been shown to moisturize the skin and reduce dryness, redness, and the appearance of inflammation. It should be applied as needed but at least twice daily.

In this study, patients will apply the cream at least twice-daily during the radiation treatments, 7 days per week.

Version: 00

Effective Date:

03-01-2018

9.6. Study Device Accountability

The Investigator is responsible for the study device accountability and record maintenance.

9.7. Study Device Handling and Disposal

Unused supplies, including the study device, will be disposed of using appropriate documentation according to International Conference on Harmonization-Good Clinical Practice (ICH-GCP), local requirements, applicable Occupational Safety and Health Administration (OSHA) and Environmental Protection Agency (EPA) regulations, and applicable study-specific procedures.

10. SCREENING ASSESSMENTS

The following assessments will be used for screening purposes only and taken after informed consent is obtained.

10.1. Demographics

Basic demographic information will be collected from the subject. This information includes age, gender, and race/ethnicity.

10.2. Medical History

Each subject will provide a brief medical history (e.g. history of allergic reactions to ensure they meet the inclusion/exclusion criteria). Study personnel will review the completed medical history form prior to enrolling the subject in the study. Study personnel may ask the subject for additional information, as necessary.

11. STUDY ENDPOINTS

11.1. Feasibility

Feasibility is the compliance rate, defined as the average number of applications per week. Participants may track applications in their daily diaries to assist in reporting to their physician at the weekly evaluation visit.

11.2. Skin Appearance

The appearance of the skin (including dryness, appearance of inflammation, and the natural barrier) as observed and recorded by study staff as well as the patient's self-report of satisfaction with the appearance of skin during the RT and up to 10 weeks post-RT.

11.3. Quality of Life

Subject quality of life will be measured using the Dermatology Life Quality Index. Subjects will complete the index at each visit. Quality of care will also be assessed qualitatively through examination of daily diary notes.

Version: 00

Effective Date:

03-01-2018

11.4. Coverage

Coverage will be calculated using the compliance rate, the number of tubes of KeraStat Cream used, and the estimated surface area (bra size).

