1. SYNOPSIS

Name of Company:Name of Product:Type of Study:KeraNetics, LLCKeraStat® CreamClinical Proof of Concept

Title of Study: Pilot Study: KeraStat® Cream for Radiation Dermatitis

Investigator(s): [name], PhD; [name], PhD

Study Period: Estimated screening expected to start March 2018; Expected completion September 2018

Phase of Development: Design & Development (Phase 3 of Design Control)

Objective(s):

Primary:

- To assess feasibility (compliance of use)
- Collect data for designing a larger future trial evaluating KeraStat Cream

Secondary:

- To assess the safety and tolerability of KeraStat Cream in subjects at risk of radiation dermatitis
- To assess the effectiveness of KeraStat Cream compared to standard of care to manage the symptoms of radiation dermatitis in subjects being treated with radiation therapy
- To estimate amount of KeraStat Cream used per patient and coverage on skin

Methodology: This is a randomized, open label study.

Number of Subjects:

Sufficient subjects will be screened and enrolled such that 24 total subjects, 12 subjects per treatment group, will complete the study through the Follow-Up Visit. With 12 participants in each treatment group, we will be able to calculate a 95% confidence interval around the compliance rate in each group with a maximum margin of error of 0.283. Comparisons between groups for effectiveness will have 80 percent power to detect a difference of 1.2 standard deviations. Results of the current study are intended to provide descriptive endpoint data to inform the design of a future clinical evaluation of product effectiveness.

Study Overview:

Study Periods:

The length of study participation for a subject is about 8-12 weeks, depending on the length of radiation treatment. The study will extend 4-6 weeks beyond the end of radiation therapy. The study will begin with a Screening Visit during treatment planning followed by weekly assessments during radiation therapy, and a follow up visit 4-6 weeks after completion of therapy. There is a total of 5-7 visits.

Study Assessments:

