- 8. Skin disease in target irradiation area
- 9. Known allergy to the standard of care or any of the ingredients in KeraStat Cream

Test Product(s), Dose, and Mode of Administration:

Investigational: KeraStat® Cream should be applied topically to the irradiation area and 1cm beyond the border of the affected area twice daily. Expel the cream from the tube. Smooth the cream over the target area to cover with a thin layer; do not rub the cream in.

Control: The standard skin care product should be applied topically to the irradiation area and 1cm beyond the border of the affected area twice daily. Smooth the product over the target area to cover with a thin layer; do not rub the product in.

Duration of Treatment:

The length of study participation for a subject is about 8-12 weeks.

Concomitant Medication Restrictions:

Chemotherapy, steroids

Criteria for Evaluation:

Effectiveness Evaluation:

Primary

- Safety and tolerability will be evaluated throughout the study utilizing patient reported outcomes
- Adverse events will be recorded throughout the study.

Secondary

- Maximum severity of radiation dermatitis as assessed by the RTOG Criteria for Radiation-Induced Acute Skin Toxicity.
- Number of subjects with Grade I radiation dermatitis
- Number of subjects with Grade II radiation dermatitis
- Number of subjects with moist desquamation present
- Change from baseline in the Dermatology Life Quality Index

Statistical Methods:

Feasibility:

Feasibility will be determined based on the average number of applications per week for a participant. Participants who average at least 10 applications per week will be classified as compliant. A 95% confidence interval will be calculated for the observed compliance rate. Along with the compliance rate, the number of tubes of KeraStat Cream used and the estimated surface area (bra size used as a surrogate) to be covered for each participant will be used to evaluate the coverage.

Safety:

Version: 00 03-01-2018

Effective Date:

Name of Company:Name of Product:Type of Study:KeraNetics, LLCKeraStat® CreamClinical Proof of Concept

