12. STATISTICS

12.1. Description of Statistical Methods

Descriptive statistics will calculated and used to inform additional device development and to inform a power calculation for a follow on study, if required. The completion rate will be used as a measure of feasibility, with participants with an average of 10 or more applications per week being classified as compliant. A 95% confidence interval will be calculated around the estimate of compliance. After summary statistics are calculated by group, a t-test will be used to compare the two treatment groups for the effectiveness outcomes of DLQI score and RTOG score. A Fisher's exact test will be used to compare skin appearance issues between the groups. The counts for each type of adverse event will be summarized by grade and treatment group. For the KeraStat treatment group, the mean coverage will be calculated per square centimeter.

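### Coverage per square centimetre rests on a count of multiuse tubes and on bra size, neither of which measures the cream used or the skin treated, so it may be off by an unknown amount; weighing tubes is a cheap improvement.

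*Combined protocol and SAP*

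**What the plan says.** The Synopsis lists as a secondary objective: "To estimate amount of KeraStat Cream used per patient and coverage on skin". Section 5.1 repeats it.

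The calculation is described in three places:

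- Section 11.4: "Coverage will be calculated using the compliance rate, the number of tubes of KeraStat Cream used, and the estimated surface area (bra size").
- Synopsis, Statistical Methods: "the estimated surface area (bra size used as a surrogate) to be covered for each participant will be used to evaluate the coverage".
- Section 12.1: "For the KeraStat treatment group, the mean coverage will be calculated per square centimeter".

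On the amount of cream, section 9.2 says "KeraStat Cream will be provided in multiuse tubes", and section 6.5.2 has them resupplied as needed at the weekly visits. The Synopsis has the cream "applied topically to the irradiation area and 1cm beyond the border of the affected area twice daily". Section 6.1 describes the radiation target: "the targeted volume will be the ipsilateral breast with or without regional lymph nodes".

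The plan gives no tube fill weight, no rule for part-used tubes, no conversion from bra size to square centimetres, and no equation joining the three inputs.

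**The concern.** The endpoint is a ratio in physical units, amount of cream over area of skin, and both parts are measured by something coarser than the quantity wanted. The numerator is a number of tubes that are each used over many applications, so the last tube is usually part full. The denominator comes from bra size, which describes the breast. The skin to be covered is the irradiated area plus a margin, and in some women it may extend over regional nodes.

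A primary objective is to collect data for designing a larger trial. An amount per application per square centimetre is the kind of figure that would carry forward into that design. If it is off by a shared factor, averaging over about a dozen women does not correct it. The amount left in a tube also cannot be recovered once the tube has been thrown away.

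**Working it through.** **The plan's own figures.** None is stated for coverage. The precision figure in section 12.2 reproduces (1.96 × √(0.25/12) = 0.283), but it concerns the compliance rate and does not bear on coverage. What follows is a sensitivity sketch, with assumptions marked.

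**1. Tube count.** Suppose every opened tube is counted as used (assumption; the plan does not say). With N tubes recorded, true use lies above N − 1 and at or below N. The overstatement is therefore less than one tube, or less than 1/N of the recorded amount: below one half for N = 2, one third for N = 3 and one sixth for N = 6. These are upper limits. For the average, take true use as lognormal with a coefficient of variation of 40% (assumption) and round each subject up:

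| True mean use (tubes) | Mean overstatement (tubes) | As % of true use |
|---|---|---|
| 1 | 0.45 | +45% |
| 2 | 0.51 | +25% |
| 3 | 0.50 | +17% |
| 5 | 0.50 | +10% |
| 8 | 0.50 | +6% |
| 12 | 0.50 | +4% |

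The average is about half a tube throughout. How much that matters depends on tubes per subject, which the documents do not give.

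**2. The 1 cm border.** For a circular field of area A (assumption), r = √(A/π), and the border adds (1 + 1/r)² − 1 of the field.

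- A = 200 cm²: r = 7.98 cm, border adds 27%.
- A = 600 cm²: r = 13.82 cm, border adds 15%.

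If the bra-size area equalled the field without its border, amount per cm² would be overstated by the same 15% to 27%.

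**3. Nodal fields.** If these add 10% to 30% to the treated area (assumption), amount per cm² is overstated by 10% to 30% in the women who have them. The group mean is affected only in proportion to their share, which is not stated.

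**4. The conversion from bra size.** If the estimated area is f times the true area, amount per cm² is multiplied by 1/f.

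- f = 0.7: 1/0.7 − 1 = +43%.
- f = 1.25: 1/1.25 − 1 = −20%.
- f = 1.5: 1/1.5 − 1 = −33%.

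Even an area error that is right on average inflates a mean of individual ratios: with lognormal error of coefficient of variation c, E[1/error] = 1 + c². That is +4% at c = 20% and +16% at c = 40%.

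**5. Together.** As a rough guide, multiply the factors. At a true mean of 2 tubes (factor 1.25):

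- f = 1.25 gives 1.25 × 0.80 = 1.00, so the errors cancel.
- f = 1.5 gives 1.25 × 0.67 = 0.83, an understatement of 17%.
- f = 0.7 gives 1.25 × 1.43 = 1.79, an overstatement of 79%.

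The documents fix neither factor.

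**6. The third input.** Section 11.1 defines the compliance rate as average applications per week. Section 12.1 turns it into a classification at 10 or more per week. Which one enters the coverage calculation is not stated.

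**The case against.** A reader might infer that the plan counts whole tubes, that both errors push the figure upward, and that coverage will therefore be overstated. The documents do not support this. They speak of the number of tubes used and neither include nor exclude part-tubes. Sections 9.6 and 16.3 foresee accountability and return of unused device. With no conversion from bra size, the sign of the area error is unknown, and step 5 shows that it can cancel or reverse the tube error. This part of the objection stands in full.

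A reader might also infer that bra size will not be collected, because section 10.1 says "This information includes age, gender, and race/ethnicity" and the visit procedures do not mention it. That list need not be exhaustive, the CRF is defined separately (section 16.1), and the analysis text requires bra size. At most this is a missing detail.

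Two further points carry weight. The plan openly calls bra size a surrogate and the area estimated, in a pilot with a descriptive aim. And for supplying a later trial, an opened tube had to be supplied whether or not it was finished, so tubes per patient is a usable planning unit and a coarse answer to the amount-used half of the objective. Neither point rescues the figure per square centimetre, which is what section 12.1 promises.

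**Conclusion.** The concern holds in a limited form. A tube count and bra size do not measure the grams used or the area treated, and the plan supplies nothing that would link them. Coverage per square centimetre may be off by an amount, and in a net direction, that the documents do not allow to be computed. If opened tubes are counted as used, the numerator is overstated by less than 1/N of the recorded amount and by about half a tube on average. The percentages for tubes, border, nodes and area all rest on the assumed values marked above.

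Only one descriptive secondary objective in the KeraStat arm is affected. The compliance endpoint, the safety summaries and the comparisons between groups do not depend on it. This is a cheap improvement and does not threaten the trial.

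**What to change.** Have KeraStat subjects bring back all opened and unopened tubes. Weigh tubes at dispensing and at return, and replace the tube count with grams used per subject. Report grams per recorded application per square centimetre, and write the equation into section 11.4, naming the number of applications as the input.

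For area, use the treated skin area plus the 1 cm border where it can be read from existing treatment-planning records. Section 6.1 describes a target volume, and nothing in the documents shows that planning yields a skin area, so this may not be possible for everyone. Otherwise keep bra size, state the conversion, and label the result as based on a surrogate.

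The cost is a scale, a tube-return instruction at the existing visits (none is there now), and a few CRF fields for about 13 subjects (26 enrolled, half per arm). The change must be made before the first tube is dispensed. It does not remove error in self-reported applications, since diary tracking is optional under section 11.1.
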